3.2 Initial Escalation

All Initial Escalation doses will be administered by investigational site personnel to the subjects under direct supervision. Eligible subjects will be randomized and receive treatment with IP on Day 1, starting at a dose of 0.5 mg, increasing the dose at 20- to 30-minute intervals to a maximum dose of 6 mg ([Table 1](#)), according to the Schedule of Events (SOE) in [Appendix 1](#). Subjects who fail to tolerate ≥ 3 mg dose on Day 1 will be considered escalation failures and will be discontinued. Subjects who tolerate ≥ 3 mg dose on Day 1 will undergo confirmatory dosing of a single 3 mg dose on the following day, Day 2. Subjects who do not tolerate this confirmatory dose will be discontinued. Subjects who tolerate this confirmatory dose will enter the Up-Dosing Period.

Table 1: Initial Escalation Schedule

Initial Escalation Schedule		
Day 1 Dose Number	Investigational Product Dose, mg ^a	Cumulative Dose, mg
1	0.5	0.5
2	1	1.5
3	1.5	3
4	3	6
5	6	12
Day 2 Dose Number	Investigational Product Dose, mg	Cumulative Dose, mg
1	3	3

^a All mg doses shown refer to milligrams of peanut protein or the equivalent placebo dose.

Doses will be delivered at 20 to 30 minute intervals under direct observation.

Capsules are to be opened, contents sprinkled over an age-appropriate food, and mixed thoroughly and consumed.

Day 1: Subjects who are unable to tolerate at least a single dose of 3 mg at the end of Day 1 will be considered escalation failures. Subjects who tolerate ≥ 3 mg on Day 1 will return on Day 2 to receive a 3 mg single dose.

Day 2: Subjects with either no symptoms or mild symptoms on Day 2 at 3 mg will start daily home-dosing at 3 mg on Day 3.

Subjects with moderate or severe symptoms at 3 mg on either Day 1 or Day 2 will be considered escalation failures and will be discontinued from the study.

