3.3 Up-Dosing

Subjects will receive IP starting at a dose of 3 mg once daily and will gradually escalate every 2 weeks to a maximum of 300 mg once daily, according to the Up-Dosing Schedule ([Table 2](#)). All first escalation doses will be administered under direct observation in the clinical research center (CRC) or other monitored setting (unless required by a specific institution, no distinction will be drawn between an investigational site, study center office, clinic, or CRC, provided the requirements for monitoring and emergency intervention are met by the facility). Subsequent doses will be dispensed to the parent/guardian and administered at home. Doses may be adjusted for tolerability or inter-current illness by the Investigator, except no down-dosing below 3 mg/day is allowed. The allowed dose levels are shown in [Table 2](#). Up-dosing may thereby be extended to a maximum of 40 weeks in order to reach 300 mg and should not exceed this period.

Subjects unable to escalate to 300 mg within 40 weeks will be considered escalation failures. Subjects able to escalate to 300 mg will continue taking the 300 mg dose for an additional 2 weeks to ensure tolerability prior to exiting ARC007. If the subject is unable to tolerate the 300 mg dose for the 2-week period, dosing may continue up to a maximum of 48 weeks after Day 1 to ensure tolerability prior to exiting the study.

Table 2: Up-Dosing Schedule

Up-Dosing Schedule			
Dose Number	Investigational Product Dose, mg	Interval (weeks)	Percent Increase from Previous Dose
1	3	2 ^a	n/a
2	6	2	100
3	12	2	100
4	20	2	67
5	40	2	100
6	80	2	100
7	120	2	50
8	160	2	33
9	200	2	25
10	240	2	20
11	300	2 ^b	25

^a Interval includes Day 2 of Initial Escalation.

^b If the subject is unable to tolerate the 300 mg dose for the 2-week period, dosing may continue up to a maximum of 48 weeks after Day 1 to ensure tolerability prior to exiting the study.

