6.3.3 Up-Dosing (Also Referred to as Build-up) Visits

Up-dosing will last from a minimum of 20 weeks to a maximum of 40 weeks and comprise 10 scheduled up-dosing visits (including the first 300 mg dose of the IP), with the potential for unscheduled visits for assessment of dose tolerability, dose reduction, dose re-escalation, or management of AEs. Subjects reaching this dose will continue in the study for an additional 2 weeks to ensure tolerability of the 300 mg/d dose. If the subject is unable to tolerate the 300 mg dose for the 2-week period, dosing may continue up to a maximum of 48 weeks after Day 1 to ensure tolerability prior to exiting the study.

Subjects will return to the clinic every 2 weeks for up-dosing to a maximum daily dose of 300 mg. The first dose of IP at each new dose level will be administered in the CRC under direct observation and medical supervision.

Subjects must be free from active wheezing, a flare of atopic disease (eg, atopic dermatitis), or suspected inter-current illness prior to any dose escalation. Subjects should be maintained on their current, or a reduced, dose level of IP until their flare of asthma, atopic disease, or inter-current illness has resolved.

Subjects should withhold their daily home dose of IP on in-clinic dosing days, but should take all other prescribed medications as scheduled.

Some or all of the following assessments/procedures will be completed during up-dosing visits in the CRC, according to the SOE:

- Return unused capsules to the clinic
- Monitoring for compliance
- Concomitant medication review
- Limited physical examination
- Diet (food allergen exposure) history update
- Pre-dose vital sign measurement (BP, PR, body temperature)
- PEFR (3 attempts are to be performed). Airflow assessment should as far as possible be measured at the same time at each visit.
- IP administration under observation in the clinic
- Post-dose vital sign measurements (BP, PR) within 15 to 30 minutes post-dose, prior to discharge, and at the Investigator's discretion during the post-dose observation period.
- Optional saliva collection at Week 6 Up-dosing Visit ([Appendix 7](#))
- Monitoring for AEs, including allergic symptoms (Section [7.2](#))
- Completion of the Total Nasal Symptom Score Sheet in subjects with allergic rhinitis ([Appendix 8](#))
- Subjects will be reminded to continue to follow a peanut-avoidant diet for the duration of the study.
- Take home capsules for daily dosing until next visit

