7.9.2 Individual Stopping Rules

Individuals may stop the study at any time by withdrawing their consent if they experience subjectively intolerable AEs, dosing symptoms, or for any other reason. In addition, > 7 consecutive days of missed daily dosing due to non-compliance (ie, for any reason other than treatment of an AE or an IP dispensing error) constitutes an individual stopping rule. During Up-dosing, subjects must halt up-dosing and re-start with a reduced dose if more than 4 days of dosing are missed. Missing 3 or more consecutive days on 3 occasions is an individual stopping rule, as is missing 15 or more consecutive days of dosing for any reason, with one exception of the voluntary 4-week hiatus for GI AEIs occurring at or before the 20 mg dose, as specified in Section 6.5.3.2.

Occurrence of any of the following will result in the cessation of dosing and the subject being discontinued from the study as an escalation failure non-responder, resulting in an Early Discontinuation Visit within 14 days:

- Failure to accomplish up-dosing of IP after 3 attempts
- Failure to identify a tolerated dose of IP after 3 attempts at dose reduction

Finally, administration of 3 or more doses of epinephrine for the treatment of any dose-related allergic reaction in any subject is an individual stopping rule.

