### 9.5 Extent of Exposure and Compliance

Study treatment exposure will be summarized for the safety population by age group (4-11 years, 12-17 years, 4-17 years), treatment group (AR101, placebo) and study period (initial escalation, up-dosing, 300 mg QD, and overall).

First and last dose dates for each study period will be identified as follows:

Study Period	First Dose Date	Last Dose Date
Initial escalation	Date of first dose at the study site on initial escalation day 1	Date of last dose at initial escalation day 1 or day 2 at the study site
Up-dosing	The day following the date study product was dispensed at initial escalation day 2	Date of first dose of 300 mg at the end of the up-dosing 300 mg visit if dose is tolerated and subject continues to at-home 300 mg QD dosing. If first in-clinic 300 mg dose is not tolerated and dose is immediately reduced, the last dose date of up-dosing will be when the first in-clinic 300 mg dose is tolerated and subject continues to at-home 300 mg QD dosing. For subjects who do not reach the 300 mg dose, the latest of the last dose during up-dosing at the study site and the last dose at home
300 mg QD	Date of first dose of study product of 300 mg at home. This is defined as the day following the first in-clinic visit where the 300 mg dose was tolerated and 300 mg study product was first dispensed.	Date of last dose of study product for subjects who enter 300 mg QD study period
Overall	Date of first dose at the study site on initial escalation day 1	Last dose of study product prior to exit visit in ARC007

The total amount of study product consumed will be calculated as the sum of doses at the study site plus the sum of doses taken at home as recorded in the dosing diary.

The following calculations of study product exposure will be made and summarized:

- Duration of exposure (in days and in months): calculated as the date of the last dose of study product minus the date of the first dose of study product plus 1 during the study period, except for initial escalation, the duration of exposure will only be 1 or 2 days depending on whether study product was taken on initial escalation day 1 and initial escalation day 2. Duration of exposure will be summarized using descriptive statistics for continuous endpoints and categorically by 28-day increments for the overall treatment period:  $\leq 28$  days, 29–56 days, ... 337–364 days, and  $> 364$  days.

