- Total dose consumed (mg): calculated as the cumulative sum of all doses taken during the study period.
- Average dose per day (mg): calculated as the total dose consumed divided by the number of days during the study period.
- Number of unsuccessful dose increases: where an unsuccessful dose increase is defined as a single dose at the study site at a higher dose level followed by an immediate return to the previous dose level or a lower dose level.
- Number of dose reductions: where a dose reduction is defined as any decrease in dose level that does not qualify as an unsuccessful dose increase.
- Maximum dose achieved (mg/day): summarized using descriptive statistics for continuous endpoints and categorically using all possible dose levels: 0.5, 1, 1.5, 3, 6, 12, 20, 40, 80, 120, 160, 200, 240, or 300 mg/day.
- Time to 300 mg dosing and time to 80 mg dosing for the overall treatment period using Kaplan-Meier methodology. Time will be calculated as date of the first 300 mg (or 80 mg) dose minus the first dose date +1. Subjects who do not reach the specified dose will be censored at the date of their last study product dose.

The nonmissing valid diary entries will be used to estimate dosing compliance at home. The following measures of compliance with dosing at home will be calculated:

- Total number of planned dosing days at home: calculated as the number of days where a valid diary entry was made, but excluding entries where a dose was missed because of investigator orders.
- Percentage of planned dosing days where a full or partial dose was consumed.
- Percentage of planned dosing days where a full dose was consumed.
- Percentage of planned dosing days where a partial dose was consumed.
- Percentage of planned dosing days where a dose was missed.

Data for dosing at home will be listed. Daily diary records, including date and time, whether a full or partial dose was consumed (or the dose was missed), and the reason for partial or missed doses will be listed. If any dose-related allergy symptoms are present, the symptoms and medications to treat the symptoms will also be listed.

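### Kaplan-Meier time to 300 mg and to 80 mg censors subjects who have stopped dosing for good, so a probability read from the curve can exceed the share of the arm that reached the dose

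*SAP*

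**What the plan says.** The exposure section of the SAP (9.5) lists "Time to 300 mg dosing and time to 80 mg dosing for the overall treatment period using Kaplan-Meier methodology". Time runs from the first dose of study product to the first 300 mg (or 80 mg) dose. For everyone else the rule is: "Subjects who do not reach the specified dose will be censored at the date of their last study product dose". It does not distinguish reasons for stopping and names no competing-risk method.

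The same section covers the crude picture: "Maximum dose achieved (mg/day): summarized using descriptive statistics for continuous endpoints and categorically using all possible dose levels". The population is the same for both outputs: "Study treatment exposure will be summarized for the safety population by age group".

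The protocol settles what happens to subjects who do not reach the dose:

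- Protocol 3.2: "Subjects with moderate or severe symptoms at 3 mg on either Day 1 or Day 2 will be considered escalation failures". They are discontinued.
- Protocol 3.3: "Subjects unable to escalate to 300 mg within 40 weeks will be considered escalation failures". The Treatment Description in the synopsis adds that subjects who miss 300 mg by week 40 are discontinued from ARC007.
- Protocol 7.9.2: three failed up-dosing attempts, or three failed attempts to find a tolerated dose by reduction, "will result in the cessation of dosing and the subject being discontinued from the study as an escalation failure non-responder".

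SAP 8 places the final analysis after all subjects have completed their exit or early termination assessments.

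**The concern.** Kaplan-Meier treats a censored subject as someone who would go on to have the event at the same rate as those still under observation. A child who has left dosing cannot reach 300 mg or 80 mg in this study. Because the analysis waits for everyone to finish, there is no administrative cut-off to account for the censoring: it is essentially all permanent stopping, often for intolerance.

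The dosing schedule adds to the effect. Protocol 6.3.3 says "Up-dosing will last from a minimum of 20 weeks to a maximum of 40 weeks and comprise 10 scheduled up-dosing visits", so the first 300 mg dose comes at about week 20. Protocol 6.3.4 puts the 80 mg visit at about week 10. A subject who stops before the first event, including every Day 1 or Day 2 escalation failure, leaves the risk set without influencing the curve.

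At stake is the reading of a tolerability result. How many children get to 300 mg bears directly on the primary objective of safety and tolerability, and one report could show two different answers for the same population.

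**Working it through.** **The plan's own figure.** There is none to reproduce. ARC007 gives no expected share reaching either dose and no distribution of stop times. The shares and timings below are assumptions.

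**Direction.** Kaplan-Meier passes the weight of each censored subject on to those still at risk. If any event follows, part of that weight ends up on events. The estimate therefore cannot fall below the crude share, and it rises above it as soon as one non-reacher stops before the last event. This needs no assumption about rates.

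**A small count.** Protocol Appendix 7 reports that 6 of 29 AR101 subjects in ARC001 discontinued. Some may have reached 300 mg first, so this gives only an order of size. Take 23 of 29 reaching the dose, a true share of 23/29 = 79.3%.

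- All 6 stop before the first event: 23/23 = 100%.
- 4 stop before the first event and 2 after the last: 23/25 = 92.0%.

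**Closed form.** Let p be the true share and f the fraction of non-reachers still dosing at week 40, the rest having stopped before the first event. The risk set at the first event is then p + (1-p)f of the arm. Nobody is censored between the first and last event, so

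estimate = p / (p + (1-p)f).

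| True share p | f = 0 | f = 0.25 | f = 0.5 | f = 1 |
|---|---|---|---|---|
| 80% | 100% | 94.1% | 88.9% | 80% |
| 90% | 100% | 97.3% | 94.7% | 90% |

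For example, 0.80/(0.80 + 0.20 × 0.5) = 0.80/0.90 = 88.9%.

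**Day 1-2 failures alone.** If a fraction q of treated subjects fail on Day 1 or 2 and all other non-reachers are still dosing at week 40, the estimate is 0.80/(1-q). That is 81.6%, 84.2% or 88.9% for q = 2%, 5% or 10%.

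**Stops spread evenly.** This was simulated with 333 subjects (two thirds of 500). Reachers arrive at week 20 plus an exponential delay in 2-week steps, truncated at week 38. With stops uniform over weeks 0-40, a true 80% shows as 93.6% at a mean delay of 3 weeks and 97.3% at 6 weeks.

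**80 mg.** The same formula at a true 85% gives 100%, 95.8%, 91.9% and 85% for f = 0, 0.25, 0.5 and 1, with f now the fraction of non-reachers who stop only after the last 80 mg event.

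**Median.** At a true 80% and f = 0, the Kaplan-Meier median equals the cumulative-incidence median at a mean delay of 3 weeks (22 and 22 weeks) and is 2 weeks earlier at 6 weeks (22 against 24). At a true 70%, f = 0 and a mean delay of 8 weeks, it is 24 against 28 weeks.

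**Check on the alternative.** In one simulated arm with 266 of 333 reaching 300 mg and stops uniform over weeks 0-40, the Aalen-Johansen estimate was 79.9%, the same as the crude share (266/333 = 79.9%). Kaplan-Meier gave 94.8%.

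**The case against.** The case for leaving the text alone has four parts.

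1. *The true share is reported anyway*: under maximum dose achieved in SAP 9.5, and closely by the number and percentage entering each study period in SAP 9.1. This stands, and it limits the importance. It does not correct the curve.
2. *Nothing rests on it.* Time to dose is not among the endpoints in SAP 4, and Protocol 9 plans no hypothesis test or between-group comparison. This also stands.
3. *The SAP does not say that a probability will be shown*, and time to dose while dosing continues is a fair descriptive question. This stands in part. If only a median is given, the effect is usually small. But a plotted curve invites a probability reading, and nothing in the SAP labels it as conditional on continued dosing.
4. *The sizes depend on assumed stop times.* They do. The week-40 placement of late stops is not the worst case, however. With half the stops late, a true 80% shows as 88.9% if those are at week 40, and as 94-98% if they are spread over weeks 20-40.

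A reader might go further and infer that the AR101-placebo difference is biased in a known direction. The documents do not support that, because they give no stop times by arm. With true shares of 80% and 95%, the 15-point gap becomes 20 points if all AR101 stops are late and all placebo stops early (80% against 100%), and -5 points in the reverse case (100% against 95%). The plan makes no such contrast in any case.

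**Conclusion.** The censoring rule is wrong as written for any probability of reaching 300 mg or 80 mg. The upward direction within an arm follows from the estimator, from stopping being final, and from the analysis waiting for all subjects. The amount cannot be known from the documents: for an assumed true share of 80% it runs from no excess to 20 points. The shift in the median is smaller and conditional on the share and the delays.

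This is an optional improvement to a descriptive exposure summary. Two stronger readings should be avoided. One is that the report would conceal the share reaching 300 mg: the crude tables give it. The other is that the safety conclusions are compromised: no endpoint, test or sample size depends on this output.

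**What to change.** Replace the censoring sentence in SAP 9.5 with:

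> Discontinuation of dosing before the specified dose is a competing event at the date of last dose; the cumulative incidence of reaching 300 mg and 80 mg will be presented for the safety population by treatment group and age group.

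Once all subjects have finished, this is simply the cumulative proportion of the safety population that has reached the dose by each time, and the Aalen-Johansen estimator reduces to it.

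Add one clarification. The time-to-dose item counts the first dose at the level, but the SAP does not say whether a single clinic dose that is not tolerated (its unsuccessful dose increase) counts towards maximum dose achieved. State that both outputs count the first dose given at that level, tolerated or not. The final cumulative incidence then matches the maximum-dose table: the 300 mg row for 300 mg, and the rows for 80 mg and above summed for 80 mg.

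The cost is the replacement sentence and the clarification, with a standard procedure and no new data. The probability shown falls to the crude share, and no other table changes.

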5.4 Assessment of Compliance with Study Treatment and Monitoring

Daily dosing and any reaction to at-home dosing will be recorded in diary logs. Doses of IP lost or destroyed at home will also be recorded in the diary logs. All unused IP should be brought back to the clinic with each visit for reconciliation of remaining capsules with the study diary.

The site will provide 24-hour emergency contact information.

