### 7.2.1 Rules for Missing Data

All adverse events with partial/missing dates and times will be considered treatment-emergent adverse events unless a partial date clearly indicates that it occurred

before the first dose of study treatment. All therapies with partial or missing dates and times recorded on the concomitant medication or non-drug therapy case report form pages will be considered concomitant unless a partial stop date and time clearly indicates it was stopped prior to the first dose of study treatment. Start and stop dates will be imputed when partial dates are present as needed to determine treatment-emergent events and concomitant medications. No imputation will be done for a completely missing start/stop date or for subjects who did not receive study treatment.

Start dates with a missing day but with month and year populated will be imputed such that:

- If the provided month and year match the month and year for that subject's first dose date, then the first dose date will be used
- In all other cases the first day of the month will be used with the provided month and year

Start dates with a missing day and month with year populated will be imputed such that:

- If the provided year matches the year for that subject's first dose date, then the first dose date will be used
- In all other cases, January 1 will be used with the provided year

Stop dates will be imputed as follows:

- Missing day with a provided year and month will use the last day of the month
- Missing day and month with provided year will use December 31

If the imputed stop date is greater than the last study date for the subject, then the imputed date will be replaced with the last known subject date.

The reported date of the reaction on the peanut allergy history case report form page and date of diagnosis of peanut allergy will be imputed when the month or day is missing as follows:

- Missing day is set to 1 if the same year and month as the informed consent date. Otherwise it is set to 15
- Missing month and day are set to January 1 if the same year as the informed consent date. Otherwise it is set to July 1.

No imputations will be made for other missing data unless specified otherwise.

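### Home-dosing compliance is computed only over days with a valid diary entry, so it can be overstated by an amount that no planned table shows

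*SAP*

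**What the plan says.** SAP 9.5 bases home compliance on the diary alone: "The nonmissing valid diary entries will be used to estimate dosing compliance at home". The denominator, called the total number of planned dosing days at home, is "calculated as the number of days where a valid diary entry was made", with entries for doses missed on the investigator's orders taken out. The measures built on it include "Percentage of planned dosing days where a full or partial dose was consumed" and "Percentage of planned dosing days where a dose was missed". A missed dose that the family records therefore counts against compliance. A day with no valid entry does not appear at all.

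Nothing elsewhere in the SAP fills the gap. SAP 7.2.1 says "No imputations will be made for other missing data unless specified otherwise", and no special rule is given for blank diary days. The SAP does not define what makes an entry valid, and it plans no count of home days without one.

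The same section defines total dose as study-site doses plus the home doses recorded in the diary. Average dose per day is then "calculated as the total dose consumed divided by the number of days during the study period".

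Protocol 5.4 expects daily dosing to be entered in the diary and provides a second source: "All unused IP should be brought back to the clinic with each visit for reconciliation of remaining capsules with the study diary". The SAP compliance measures do not use it.

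**The concern.** A planned day should be fixed by the dosing schedule. Here it is fixed by whether someone wrote something down, so the denominator depends on the behaviour being measured. A family that leaves the diary blank on days when the dose is skipped scores better than one that skips the same doses and records them.

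The section is also not consistent with itself. A blank day inside a dosing period vanishes from compliance, yet it remains in the day count for average dose per day and adds 0 mg there. A reader who sets the two results side by side has no explanation of why they differ.

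At stake is the interpretation of tolerability. The primary objective is safety and tolerability, and how much of the assigned product was actually taken is part of the context for the adverse event rates. A compliance figure that looks high only because undocumented days were dropped would mislead on that point.

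**Working it through.** **Plan's own figure.** Neither document states an expected compliance, a target or a threshold, so there is nothing to reproduce.

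**Inputs.** The denominator and dose rules come from SAP 9.5. Three quantities are not in the documents and are assumed:
- u, the share of home days (not withheld by the investigator) with no valid entry: 5%, 10% or 20%
- p, adherence on recorded days: 95%
- q, adherence on unrecorded days: 0% to 100%

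**Step 1: formulas.** Under the SAP rule, both numerator and denominator are restricted to recorded days:

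SAP compliance = (1 − u)p / (1 − u) = p

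Compliance over all home days = (1 − u)p + uq

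Difference = p − [(1 − u)p + uq] = u(p − q)

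The SAP figure does not respond to u or q. It is too high if q < p, right if q = p, and too low if q > p.

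**Step 2: numbers with p = 95%.** Each cell gives compliance over all home days, then the SAP figure minus that value in percentage points.

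| u | SAP reports | q = 0% | q = 50% | q = 95% | q = 100% |
|---|---|---|---|---|---|
| 5% | 95% | 90.25% (+4.75) | 92.75% (+2.25) | 95% (0) | 95.25% (−0.25) |
| 10% | 95% | 85.5% (+9.5) | 90.5% (+4.5) | 95% (0) | 95.5% (−0.5) |
| 20% | 95% | 76.0% (+19.0) | 86.0% (+9.0) | 95% (0) | 96.0% (−1.0) |

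For u = 10%: 0.90 × 0.95 = 0.855, and 0.855 + 0.10 = 0.955. When recorded adherence is high, nearly all the room for error is on the side of overstatement.

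**Step 3: one subject in days.** Protocol Table 2 has 11 dose levels of 2 weeks: 11 × 14 = 154 days, counting Day 2 of Initial Escalation. Taking out Day 2 and the 10 scheduled up-dosing visits leaves 154 − 11 = 143 home days. The blank and missed counts below are assumed.

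| Blank days | Recorded missed | SAP rule | Blanks counted as missed | Blanks counted as taken |
|---|---|---|---|---|
| 14 | 6 | 123/129 = 95.3% | 123/143 = 86.0% | 137/143 = 95.8% |
| 28 | 6 | 109/115 = 94.8% | 109/143 = 76.2% | 137/143 = 95.8% |
| 14 | 0 | 129/129 = 100.0% | 129/143 = 90.2% | 143/143 = 100.0% |

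Doubling the blank days moves the SAP figure by half a point and the lower bound by almost ten.

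**Step 4: average dose.** Take a subject in the 300 mg period with no in-clinic doses, 10% of days blank and a full dose on every recorded day. SAP compliance is 100%. Average dose is 0.90 × 300 = 270 mg/day. The first measure ignores the blank days and the second counts them as zero.

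**The case against.** The strongest reply is that this is an openly stated complete-case estimate. SAP 9.5 says that nonmissing valid entries are used to estimate compliance, and if diaries go blank for reasons unrelated to dosing (a lost page, for instance) the bias is zero. That stands. A reader might infer that compliance is overstated, but the documents do not show that adherence is lower on blank days, and they give no rate of blank days. Only the possibility of overstatement is established.

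A reader might also infer that the rule hides missed doses as a safety problem. The documents do not support this. The missed-dose stopping rules apply to individual subjects during the study, and none uses the SAP percentage. Study product compliance is a protocol deviation category, with major deviations summarised by arm. Reasons for discontinuation are summarised, and daily diary records are listed.

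Nor do the documents show that blank days differ between AR101 and placebo. Holds ordered by the investigator are entered in the diary and excluded, so they are not blank days. The possibility is a reason to tabulate blanks by arm, and no more.

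The two measures do not contradict each other merely by having different denominators. Average dose is an exposure measure that covers clinic and home, while compliance covers home only. What remains is that the same undocumented day is handled in two ways without explanation.

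The SAP does report both duration of exposure and the number of planned home days. Their difference, however, mixes clinic days, ordered holds and blank days, so the undocumented share cannot be read from it.

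**Conclusion.** The point holds as a limited one. The SAP's denominator removes undocumented home days, no other provision restores them, and no planned table shows how many there are. Home compliance can therefore be overstated. With the assumed 95% adherence on recorded days and 10% of days blank, the reported 95% is compatible with a true value from 85.5% to 95.5%; with 20% blank, from 76.0% to 96.0%. These ranges rest entirely on the assumed shares. If few days are blank, or if blank days are as adherent as recorded ones, little or nothing is lost.

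Only gaps inside a dosing period are affected. Days after the last dose date fall outside the period under the SAP's definitions and under the change proposed here, so a family that stops dosing and recording for good is not the case at issue.

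The consequence is modest. Compliance is descriptive, is not a primary, secondary or exploratory endpoint, defines no analysis population and enters no test. This is a cheap improvement, and no planned conclusion depends on it.

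**What to change.** In SAP 9.5:

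1. Define planned home-dosing days as the calendar days in each period's home-dosing interval, using the first and last dose dates already tabulated there, minus in-clinic dosing days and investigator-ordered holds.
2. State what makes a diary entry valid, and report the number and percentage of undocumented home days by arm.
3. Give compliance twice, with undocumented days counted as missed and as taken, with equal prominence. Using the first alone as the headline would be worst-case imputation and would understate compliance if a diary were simply lost.
4. Keep the average-dose denominator as all days in the period. Its numerator includes study-site doses, so moving it to home days only would inflate the average. Add a footnote that undocumented days contribute 0 mg.
5. Use returned-capsule reconciliation as a cross-check only if the counts are in the database. Protocol 5.4 describes the reconciliation, but neither document says that the counts are captured for analysis.

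The cost of items 1 to 4 is SAP wording and programming, with no new site procedure. The downside is that a single compliance figure becomes a range, wider and possibly less favourable.
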